10.4.1. Definitions

10.4.1.1. Woman of childbearing potential (WOCBP)

A woman is considered WOCBP (fertile) from the time of menarche until becoming postmenopausal unless permanently sterile (see below).

Note: Menarche is the first onset of menses in a young female. Menarche is normally preceded by several changes associated with puberty including breast development and pubic hair growth.

10.4.1.2. Woman of Nonchildbearing potential (WONCBP)

Women in the following categories are considered WONCBP:

- Premenopausal female permanently sterile due to one of the following procedures:
 - Documented hysterectomy
 - Documented bilateral salpingectomy
 - Documented bilateral oophorectomy

For permanently sterile individuals due to an alternate medical cause other than the above, (e.g., Mullerian agenesis, androgen insensitivity, gonadal dysgenesis), investigator discretion should be applied to determining study entry. If reproductive status is questionable, additional evaluation should be considered.

Note: Documentation can come from the site personnel's review of the participant's medical records, medical examination, or medical history interview.

Postmenopausal female

A postmenopausal state is defined as no menses for 12 months without an alternative medical cause.

- A high FSH level in the postmenopausal range may be used to confirm a
 postmenopausal state in women not using hormonal contraception or HRT.
 However, in the absence of 12 months of amenorrhea, confirmation with more
 than one FSH measurement is required.
- Females on HRT and whose menopausal status is in doubt must discontinue
 HRT to allow confirmation of postmenopausal status before study enrollment.

10.4.2. Contraception guidance

10.4.2.1. Woman of childbearing potential (WOCBP)

Female participants of childbearing potential are eligible to participate if they agree to use a highly effective contraceptive method consistently and correctly according to the methods listed in GSK's list of highly effective contraceptive methods (Table 20).

Table 20 Highly effective contraceptive methods

Highly Effective Contraceptive Methods That Are User Dependent a Failure rate of <1% per year when used consistently and correctly

Combined (estrogen- and progestogen-containing) hormonal contraception associated with inhibition of ovulation

- Oral^b
- Intravaginal
- Transdermal

Progestogen-only hormonal contraception associated with inhibition of ovulation

- Injectable
- Oral^b (only if allowed by local regulations or if part of standard medical practice in the country)

Highly Effective Methods That Are User Independent

- Implantable progestogen-only hormonal contraception associated with inhibition of ovulation
- Intrauterine device (IUD)
- Intrauterine hormone-releasing system (IUS)
- Bilateral tubal occlusion/ligation

Vasectomized partner

(A vasectomized partner is a highly effective contraception method provided that the partner is the sole male sexual partner of the WOCBP and the absence of sperm has been confirmed. If not, an additional highly effective method of contraception should be used.)

Male partner sterilization prior to the female participant's entry into the study, and this male is the sole partner for that participant,

(The information on the male sterility can come from the site personnel's review of the participant's medical records; medical examination and/or semen analysis, or medical history interview provided by her or her partner)

Sexual abstinence

(Sexual abstinence is considered a highly effective method only if defined as refraining from heterosexual intercourse during the entire period of risk associated with the study drug. The reliability of sexual abstinence needs to be evaluated in relation to the duration of the study and the preferred and usual lifestyle of the participant).

10.5. Appendix 5: Country-specific requirements

Not applicable.

^a Typical use failure rates may differ from those when used consistently and correctly. Use should be consistent with local regulations regarding the use of contraceptive methods for subjects in clinical studies.

^b For WOCBP taking hormonal contraception, an additional barrier contraception method is recommended if they are concomitantly taking drugs that interact and reduce effectiveness of hormonal contraception. The investigator should check the list of drugs that could reduce hormonal contraceptive effectiveness (Potent drug enzyme inducers).

SAP Amendment 1	23 July 2024	Protocol v4.0 (09 January 2024)	Section 4.2.2: Add precision that the RSV-A/RSV-B primary analysis will be based on ED60 units. Section 4.3.1: Addition of RSV-A/RSV-B secondary analysis based on IU/mL units. Remove graph for MGI. Section 4.4.1: Removal of tables for demyelinating disorder AEs Reformatting the paragraph and clarifying the analyses performed by	Section 4.2.2: Clarification on the unit used for RSV-A/RSV-B primary endpoints. Section 4.3.1: Addition of RSV-A/RSV-B immunogenicity analysis on IU/mL to align at Project level. No graph will be produced for MGI. Section 4.4.1: Demyelinating disorder AEs will be part of overall AE tables showing different SMQs. Clarification of safety analyses performed by dose and overall.

SAP Version	Approval Date	Protocol Version (Date) on which SAP is Based	Change	Rationale
			dose and overall. Section 6.1.2: Add age category, ≥ 60 YOA & ≥ 80 YOA. Add sentence on potential requirement for deidentified displays. Section 6.2: Appendix added for eCOA compliance	Section 6.1.2: To align age category presented in demography table with age category used in subgroup analyses. Deidentification of public disclosure to ensure data privacy of clinical trials participants. Section 6.2: Updated SAP template – Not applicable as assessment collected via paper diary
SAP Amendment 2	12 December 2024	Protocol v4.0 (09 January 2024)	Section 3.1.3: Change elimination code 2080 to eliminate from the specific visit at which the condition is met onwards. Section 6.3.5: Modify	Section 3.1.3: Correction for elimination code Section 6.3.5: Alignment with project specific definition for missing/partial dates.

SAP Version	Approval Date	Protocol Version (Date) on which SAP is Based	Change	Rationale
			imputation rule for AE end dates with missing day and month	
SAP Amendment 3	24 Mar 2025	Protocol v4.0 (09 January 2024)	Section 4.1.1: Modify the imputation rule for values below LLOQ in the reverse cumulative curves Section 4.6.1: Modify the sequence of analysis Section 4.7: Including the modifications in the sequence of analysis	Section 4.1.1: Alignment with project specific imputation rules for the reverse cumulative curves Section 4.6.1: Add the possibility of performing a combined analysis in case of delay in lab data availability Section 4.7: Add the possibility of performing a combined analysis in case of delay in lab data availability

1. INTRODUCTION

The purpose of this SAP is to describe the planned statistical analyses to be included in the clinical study report (CSR) for Study RSV-OA=ADJ-013 (217848).

1.1. Objectives, Estimands and Endpoints

	Objectives	Endpoints			
		Pri	mary		
•	To demonstrate non-inferiority* of humoral immune response to RSVPreF3 OA investigational vaccine when co-administered with a COVID-19 mRNA vaccine compared to RSVPreF3 OA investigational vaccine administered alone.	•	RSV-A neutralization titers expressed as group GMT ratio 1 month after the RSVPreF3 OA investigational vaccine dose. RSV-B neutralization titers expressed as group GMT ratio 1 month after the RSVPreF3 OA investigational vaccine dose.		
•	To demonstrate non-inferiority* of humoral immune response to a COVID-19 mRNA vaccine when co-administered with the RSVPreF3 OA investigational vaccine compared to COVID-19 mRNA vaccine administered alone.	•	SARS-CoV-2 Omicron XBB.1.5 neutralization titers against pseudovirus bearing S protein expressed as group GMT ratio 1 month after the COVID-19 mRNA vaccine.		
		Seco	ondary		
•	To evaluate the humoral immune response to RSVPreF3 OA investigational vaccine when co-administered with a COVID-19 mRNA vaccine or administered alone.	•	RSV-A neutralization titers expressed as GMT, MGI and SRR at 1 month after the RSVPreF3 OA investigational vaccine dose. Percentage of participants having RSV-A neutralizing titers ≥ assay cut-off (i.e., LLOQ) at pre-vaccination and 1 month after the RSVPreF3 OA investigational vaccine dose. RSV-B neutralization titers expressed as GMT, MGI and SRR at 1 month after the RSVPreF3 OA investigational vaccine dose. Percentage of participants having RSV-B neutralizing titers ≥ assay cut-off (i.e., LLOQ) at pre-vaccination and 1 month after the RSVPreF3 OA investigational vaccine dose.		
•	To evaluate the humoral immune response to a COVID-19 mRNA vaccine when coadministered with the RSVPreF3 OA investigational vaccine or administered alone.	•	SARS-CoV-2 Omicron XBB.1.5 neutralization titers against pseudovirus bearing S protein expressed as GMT and MGI at 1 month after the COVID-19 mRNA vaccine. Percentage of participants having SARS-CoV-2 Omicron XBB.1.5 neutralization titers ≥ assay cut-off (i.e., LLOQ) at pre-vaccination and 1 month after the COVID-19 mRNA vaccine dose.		

Objectives	Endpoints
To evaluate the safety and reactogenicity following administration of the RSVPreF3 OA investigational vaccine and a COVID-19 mRNA vaccine, co-administered or administered alone.	 Percentage of participants reporting each solicited administration site event and systemic event within 4 days post study intervention administration (i.e., the day of vaccination and 3 subsequent days). Percentage of participants reporting unsolicited AEs within 30 days post study intervention administration (i.e., the day of vaccination and 29 subsequent days). Percentage of participants reporting SAEs after study intervention administration (Day 1) up to study end (6 months after last study intervention administration). Percentage of participants reporting pIMDs after study intervention administration (Day 1) up to study end (6 months after last study intervention administration).

AE: adverse event; GMT: Geometric Mean Titer; MGI: Mean Geometric Increase; pIMD: potential immune mediated disease; SAE: serious adverse event, SRR: Seroreponse rate. MGI and SRR are defined in Section 4.1.1

1.1.1. Estimands

1.1.1.1. Immunogenicity Objectives

The primary question of interest is to demonstrate the non-inferiority of the humoral immune response after RSVPreF3 OA investigational vaccine co-administered with a dose of COVID-19 mRNA vaccine when compared to RSVPreF3 OA investigational vaccine administered alone and COVID-19 mRNA vaccine administered alone, in adults aged 50 years vaccinated as per protocol.

The secondary objectives are the following:

- To evaluate the humoral immune response to RSVPreF3 OA investigational vaccine when co-administered with a dose of COVID-19 mRNA vaccine or when administered alone.
- To evaluate the humoral immune response to a dose of COVID-19 mRNA vaccine when co-administered with the RSVPreF3 OA investigational vaccine or when administered alone.

^{*} Non-inferiority criteria are defined in Section 4.2.2

Attributes							
Objectives	Treatment	Population	Endpoint (Variable)	Intercurrent events (ICE		Summary measure	
Objectives	rreaument	Population	Endpoint (variable)	Description	Handling strategy		
Primary	Co-ad group: COVID-19 mRNA vaccine at Day 1 and RSVPreF3 OA investigational vaccine at Day 1 Control group: COVID-19 mRNA vaccine at Day 1 and RSVPreF3 OA investigational vaccine at Day 31	Adults ≥ 50 years at the time of first vaccination	RSV-A and RSV-B neutralizing titers measured at 1 month (at Day 61 for Control group, at Day 31 for Co-ad group) after RSVPreF3 OA investigational vaccine administration). SARS-CoV-2 Omicron XBB.1.5 neutralization titers measured at 1 month (at Day 31 for both groups) after COVID-19 mRNA vaccine administration.	Study vaccination not administered as per protocol. Prohibited medication, vaccination or intercurrent medical condition prior to the blood sample.	Data collected after ICEs will be excluded from the analysis. (Hypothetical strategy) Rationale: To evaluate the immunogenicity parameters in the absence of ICE	 Ratio of GMTs with 95% CI for RSV-A and RSV-B neutralizing titers 1 month after RSVPreF3 OA investigational vaccine administration between the Control group versus Co-ad group. Ratio of GMTs with 95% CI for SARS-CoV-2 Omicron XBB.1.5 titers 1 month after COVID-19 mRNA vaccine administration between the Control group versus Co-ad group. 	
Secondary	Co-ad group: COVID-19 mRNA vaccine at Day 1 and RSVPreF3 OA investigational vaccine at Day 1 Control group: COVID-19 mRNA vaccine at Day 1 and RSVPreF3 OA investigational vaccine at Day 31	Adults ≥ 50 years at the time of first vaccination	RSV-A and RSV-B neutralizing titers measured at prevaccination (at Day 1 for Co-ad group and at Day 31 for Control group) and at 1 month (at Day 31 for Co-ad group and at Day 61 for Control group) after RSVPreF3 OA investigational vaccine administration. Fold increase in RSV-A and RSV-B neutralizing titers from pre-vaccination to 1-Month post RSVPreF3-OA	Study vaccination not administered as per protocol. Prohibited medication, vaccination or intercurrent medical condition prior to the blood sample.	Data collected after ICEs will be excluded from the analysis. (Hypothetical strategy) Rationale: To evaluate the immunogenicity parameters in the absence of ICE	 GMTs with 95% CI for RSV-A and RSV-B neutralizing titers at prevaccination and at 1 month after RSVPreF3 OA investigational vaccine dose administration. MGI with 95% CI for RSV-A and RSV-B neutralizing titers at 1 month after RSVPreF3 OA investigational vaccine dose administration Percentage of participants having RSV-A and RSV-B neutralizing titers ≥ cut-off and 95% CI at prevaccination and 1 month 	

			Summary measure			
Objectives Treatment Population					Endneint (Verieble)	Intercurrent events (ICEs)
Objectives	Treatment	Population	investigational vaccine administration. RSV-A and RSV-B neutralizing titers ≥ assay cut-off at pre-vaccination and 1 month after the RSVPreF3 OA investigational vaccine dose administration. Seroresponse in RSV-A and RSV-B, defined as a fold increase in neutralizing titers from pre-vaccination to 1-Month post RSVPreF3-OA investigational vaccine administration ≥4.	Description	Handling strategy	after the RSVPreF3 OA investigational vaccine dose administration. • Seroresponse rate (SRR) with 95% CIs for RSV-A and RSV-B, defined as the proportion of participants having a fold increase in neutralizing titers from prevaccination to 1-Month pos RSVPreF3-OA investigational vaccine administration ≥4.
Secondary	Co-ad group: COVID-19 mRNA vaccine at Day 1 and RSVPreF3 OA investigational vaccine at Day 1 Control group: COVID-19 mRNA vaccine at Day 1 and RSVPreF3 OA investigational vaccine at Day 31	Adults ≥ 50 years at the time of first vaccination	SARS-CoV-2 Omicron XBB.1.5 neutralization titers measured at prevaccination (at Day 1) and at 1 month (at Day 31) after COVID-19 mRNA vaccine administration. Fold increase in SARS-CoV-2 Omicron XBB.1.5 neutralization titers from pre-vaccination to 1-Month post COVID-19 mRNA vaccine administration.	Study vaccination not administered as per protocol. Prohibited medication, vaccination or intercurrent medical condition prior to the blood sample.	Data collected after ICEs will be excluded from the analysis. (Hypothetical strategy) Rationale: To evaluate the immunogenicity parameters in the absence of ICE	GMTs with 95% CI for SARS-CoV-2 Omicron XBB.1.5 neutralizing titers at pre-vaccination and at 1 month after COVID-19 mRNA vaccine dose administration. MGI with 95% CI for SARS CoV-2 Omicron XBB.1.5 neutralizing titers at 1 month after COVID-19 mRNA vaccine dose administration.

[figure not shown]
	Attributes							
Objectives	Treatment	Population	Enc	dpoint (Variable)	Intercurrent events (ICE	s)	Summary measure	
Objectives	rreaument	Population	EIIC	apoint (variable)	Description	Handling strategy		
			•	SARS-CoV-2 Omicron XBB.1.5 neutralizing titers ≥ assay cut-off at prevaccination and 1 month after the COVID-19 mRNA vaccine vaccine dose administration.			•	Percentage of participants having SARS-CoV-2 Omicron XBB.1.5 neutralizing titers ≥ cut-off and 95% CI at pre-vaccination and 1 month after the COVID-19 mRNA vaccine dose administration.

1.1.1.2. Safety Objectives

The secondary question of interest is to evaluate the safety and reactogenicity following administration of the RSVPreF3 OA investigational vaccine and a dose of COVID-19 mRNA vaccine, co-administered or administered alone.

	Attributes								
Treatment Population		Endpoint (Variable)	Intercurrent events (ICEs)	Summary measure					
Treatment	Population	Enupoint (variable)	Description Handling stra	ategy					
Co-ad group: COVID- 19 mRNA vaccine at Day 1 and RSVPreF3 OA investigational vaccine at Day 1 Control group: COVID-19 mRNA vaccine at Day 1 and RSVPreF3 OA investigational vaccine at Day 31	Adults ≥50 years at the time of first vaccination	 Occurrence of each solicited administration site event with onset within 4 days after study intervention administration. Occurrence of each solicited systemic event with onset within 4 days after study intervention administration. Occurrence of unsolicited AEs within 30 days after study intervention administration. Occurrence of SAEs after study intervention administration (Day 1) up to study end (6 months after last study intervention administration administration (Day 1) up to study end (6 months after last study intervention administration). 	Study vaccination not administered as per protocol. Prohibited regardless of medication, vaccination or intercurrent medical condition prior to the blood sample. All the data of for the varial interest are or regardless of whether the intercurrent occurs (treat policy).	collected The percentage of participants by group who report each of the endpoint.					

1.2. Study Design

2. STATISTICAL HYPOTHESES

Statistical hypotheses are associated to the confirmatory primary non-inferiority (NI) objectives, which will be tested to control overall Type I error. Global Type I error is controlled at 2.5% (1-sided). The study includes three confirmatory primary objectives. The NI margins associated to each objective are provided in Table 1.

Table 1 Study Objectives and Null Hypothesis

Objectives	Null hypothesis	Success criteria
Primary		
To demonstrate non-inferiority of humoral immune response to RSVPreF3 OA investigational vaccine when co-administered with a COVID-19 mRNA vaccine compared to RSVPreF3 OA investigational vaccine administered alone.	True Group GMT ratio between Control group (at Day 61) divided by Co-ad group (at Day 31) for RSV-A neutralization titers 1-month after the RSVPreF3 OA investigational vaccine dose is above 1.5. True Group GMT ratio between Control group (at Day 61) divided by Co-ad group (at Day 31) in RSV-B neutralization titers 1-month after the RSVPreF3 OA investigational vaccine dose is above 1.5.	The upper limit of the 2 sided 95% CI of the GMT ratio between the Control group (at Day 61) versus Co-ad group (at Day 31) for RSV-A neutralization titer 1-month after the RSVPreF3 OA investigational vaccine dose is ≤1.5. The upper limit of the 2 sided 95% CI of the GMT ratio between the Control group (at Day 61) versus Co-ad group (at Day 31) for RSV-B neutralization titer 1-month after the RSVPreF3 OA investigational vaccine dose is ≤1.5.
To demonstrate non-inferiority of humoral immune response to a COVID-19 mRNA vaccine when coadministered with the RSVPreF3 OA investigational vaccine compared to a COVID-19 mRNA vaccine administered alone.	True Group GMT ratio between Control group (at Day 31) divided by Co-ad group (at Day 31) for SARS-CoV-2 neutralization titers 1-month after the COVID-19 mRNA vaccine dose is above 1.5.	The upper limit of the 2 sided 95% CI of the GMT ratio between the Control group (at Day 31) versus Co-ad group (at Day 31) for SARS-CoV-2 neutralization titers 1-month after the COVID-19 mRNA vaccine dose is ≤1.5.

Abbreviations: Co-ad=co-administration group; Cl=confidence interval, GMT=geometric mean titer, RSV-A=respiratory syncytial virus subtype A; RSV-B=respiratory syncytial virus subtype B; RSVPreF3-OA=respiratory syncytial virus prefusion protein 3 older adult investigational vaccine.

Co-ad group: RSVPreF3 OA investigational vaccine when co-administered with the COVID-19 mRNA vaccine. Control group: Administration of COVID-19 mRNA vaccine, followed by RSVPreF3 OA investigational vaccine with one month difference.

2.1. Multiplicity Adjustment

The three confirmatory primary non-inferiority (NI) objectives will be tested simultaneously to control overall Type I error. Global Type I error is controlled at 2.5% (1-sided).

3. ANALYSIS SETS

Analysis set	Description		
Screened Set	All participants who were screened for eligibility.		
Enrolled Set [1]	All participants who entered the study (who were randomized or received study intervention or underwent a post-screening study procedure).		
Exposed Set	All participants who received the study intervention. Analysis per group is based on the administered intervention.		
RSV PPS [2]	 All eligible participants: Who received RSV vaccine as per-protocol in the control group and received all the study interventions in the Co-ad group Who had immunogenicity results pre and post-dose for RSV neutralization titers Who comply with the blood draw intervals for RSV samples Without intercurrent medical conditions that may interfere with immunogenicity and without prohibited concomitant medication/vaccination up to blood sample post RSV vaccination Who do not meet any of the criteria for elimination up to blood sample post RSV vaccination 		
COVID-19 mRNA PPS [2]	 All eligible participants: Who received a COVID-19 mRNA vaccine as per-protocol in the control group and received all the study interventions in the Co-ad group Who had immunogenicity results pre and post-dose for SARS-CoV-2 neutralization titers Who comply with the blood draw intervals for SARS-CoV-2 samples Without intercurrent medical conditions that may interfere with immunogenicity and without prohibited concomitant medication/vaccination up to blood sample post COVID-19 mRNA vaccination Who do not meet any of the criteria for elimination up to blood sample post COVID-19 mRNA vaccination 		

^[1] Screen failures (who never passed screening) and participants screened but never enrolled into the study (met eligibility but not needed to reach the target enrollment) are excluded from the Enrolled Set as they did not enter the study.

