7. DISCONTINUATION OF STUDY INTERVENTION AND PARTICIPANT DISCONTINUATION/WITHDRAWAL

7.1. Discontinuation of study intervention

Discontinuation of study intervention refers to any participant who has not received all planned doses of study intervention. In rare instances, it may be necessary for a participant to permanently discontinue study intervention. If study intervention is permanently discontinued, the participant should, if possible, continue other study procedures (e.g., safety or immunogenicity), planned in the study protocol at the discretion of the investigator.

The primary reason for premature discontinuation of the study intervention will be documented on the eCRF based on the list below:

Reasons	Additional items/Sub-reasons
	Unsolicited AE
AE	Solicited AE
	SAE/pIMDs
Lost to follow-up	0
Withdrawal by Participant	Burden of Procedure
	Participant Relocated
	COVID-19
	Other, specify
Investigator decision	Specify
Protocol Deviation	Specify
Site Terminated by Sponsor	0
Study Terminated by Sponsor	0
Pregnancy	0
Death	0
Other	Specify

AE= Adverse event; COVID-19= Coronavirus disease; pIMD= Potential immune-mediated disease; SAE= Serious adverse event.

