7.1.1. Contraindications to subsequent study intervention(s) administration

The eligibility for participants in the control group for subsequent study intervention administration must be confirmed before administering the RSVPreF3 OA investigational vaccine at Visit 2.

Participants who meet any of the criteria listed below or criteria listed in Section 5.2.1 and Section 5.2.2 should not receive the RSVPreF3 OA investigational vaccine at Visit 2. Such participants should be encouraged to continue other study procedures, at the investigator's discretion. All relevant criteria for discontinuation of study intervention administration must be recorded in the eCRF.

- Participants who experience any SAE judged to be possibly or probably related to
 the first study intervention (COVID-19 mRNA vaccine administered at Visit 1) or
 non-study concomitant vaccine/product, including hypersensitivity reactions and
 that, in the opinion of the investigator, may pose additional risk to the participant if
 he/she receives the second study intervention (RSVPreF3 OA investigational
 vaccine).
- Participants who develop any new condition which, in the opinion of the investigator, may pose additional risk to the participants if they continue to participate in the study.
- Anaphylaxis following the administration of study intervention(s).
- Condition that in the judgment of the investigator would make intramuscular injection unsafe.
- Pregnant and lactating female participant (Refer Section 8.4.6) and lactation.
- Occurrence of a new pIMD or the exacerbation of an existing pIMD that, in the opinion of the investigator, expose the participant to unacceptable risk from subsequent vaccination. In such cases, the investigator should use their clinical judgment prior to administering the next dose of the study intervention(s). Refer to Section 8.4.4.1 for the definition of pIMD.
- Occurrence of a new Adverse Event of Special Interest (AESI) or the exacerbation of an existing AESI that, in the opinion of the investigator, exposes the participant to unacceptable risk from subsequent doses of study intervention. Refer to Section 8.4.4 for the definition of AESI.

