3.1.2. Elimination from ES

The following codes will be used for identifying participants to be eliminated from the ES:

- Code 800 (Fraudulent data)
- Code 900 (Invalid informed consent)
- Code 1030 (Study intervention not administered at all)

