4.2. Primary Endpoint(s) Analyses

The primary analysis set will be the PPS. If, in any group, the percentage of vaccinated participants with serological results excluded from the PPS is more than 5%, a second analysis based on the ES will be performed to complement the PPS analysis.

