4.4. Safety Analyses

The safety analyses will be based on the ES.

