- The same computations will be done for Grade 3 AEs, for Grade 3 non-serious AEs and for AEs resulting in a medically attended visit.
 - Those analyses will present all solicited and unsolicited AEs, including SAEs and AESIs (unless otherwise specified).
- The number and percentage of participants with at least one administration site event (solicited only), with at least one systemic event (solicited only) and with any solicited event during the 4-day follow-up period after vaccination will be tabulated with exact 95% CI for each group, after each dose and overall.
- The same computations will be done for Grade 3 AEs and for AEs resulting in a medically attended visit.
- The number and percentage of participants reporting each individual solicited administration site or systemic event (any grade, Grade 3 and resulting in medically attended visit) during the 4-day follow-up period after vaccination will be tabulated with exact 95% CI for each group, after each dose and overall.
- For fever, the number and percentage of participants reporting fever by half degree (°C) cumulative increments during the 4-day follow-up period after vaccination will be tabulated for each group, after each dose and overall.
- The percentage of participants with each solicited administration site event and solicited systemic event (any grade and Grade 3) during the 4-day follow-up period after vaccination will be represented graphically for each group after each dose and overall.
- The duration in days of each individual solicited events will be tabulated using descriptive statistics (mean, min, Q1, median, Q3, maximum).
- The number of days with Grade 3 solicited events will be tabulated for each individual solicited event using descriptive statistics (mean, min, Q1, median, Q3, maximum).

- The number and percentage of participants with any unsolicited AEs during the 30-day follow-up period (i.e., the day of vaccination and 29 subsequent days) with its exact 95% CI will be tabulated by group and by Medical Dictionary for Regulatory Activities (MedDRA) Primary System Organ Class (SOC), High Level Term (HLT) and Preferred Term (PT), after each dose and overall. Similar tabulation will be done for Grade 3 unsolicited AEs, for any causally related unsolicited AEs, for Grade 3 causally related unsolicited AEs and for unsolicited AEs resulting in a medically attended visit.

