6.3.3. Assessment Window

For data summaries by visit, the nominal visit description will be used.

Analysis Set / Parameter (if applicable)		Target	Analysis Window		Analysis
Domain			Beginning Timepoint	Ending Timepoint	Timepoint
Immunogenicity	RSV-A & RSV-B Nab and SARs-COV-2 Nab (Co-ad) SARs-COV-2 Nab (control)	Day 1	Day 1	Day 1	VISIT 1
Immunogenicity	RSV-A & RSV-B Nab and SARs-COV-2 Nab (Co-ad & Control)	Day 31	Day 31	Day 42	VISIT 2
Immunogenicity	RSV-A & RSV-B Nab (Control)	Day 61	Day 61	Day 84	VISIT 3

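### Could Control participants who miss the Day 31 RSV dose bias the complementary Exposed Set analysis toward non-inferiority?

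*SAP*

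**What the plan says.** SAP section 3 defines the Exposed Set once for the whole study: "All participants who received the study intervention. Analysis per group is based on the administered intervention". SAP 3.1.2 removes a participant from it for fraudulent data, for invalid consent, or under "Code 1030 (Study intervention not administered at all"). None of these covers a Control participant who had the Day 1 COVID-19 vaccine and missed the Day 31 RSV vaccine. The RSV PPS in the same section differs: in the Control group it requires receipt of the RSV vaccine.

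The confirmatory analysis uses the PPS. If more than 5% of vaccinated participants with serology are excluded from the PPS in any group, "a second analysis based on the ES will be performed to complement the PPS analysis" (SAP 4.2, repeated in 4.3.1 for the secondary endpoints).

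Blood sampling can continue after a missed dose. Protocol 7.1 says that "the participant should, if possible, continue other study procedures (e.g., safety or immunogenicity"), and 7.1.1 says that such "participants should be encouraged to continue other study procedures". Both sentences leave this to the investigator's discretion. SAP 6.3.3 adds: "For data summaries by visit, the nominal visit description will be used".

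For safety, "The safety analyses will be based on the ES" (SAP 4.4), and unsolicited events are tabulated by System Organ Class, "High Level Term (HLT) and Preferred Term (PT), after each dose and overall" (SAP 4.4.1). SAP 6.3.5.3 states a denominator for solicited events only.

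**The concern.** The estimate is the Control GMT over the Co-Ad GMT, and success means an upper 95% limit of at most 1.5. A Visit 3 titer from a Control participant who never had the RSV vaccine is close to a baseline titer. Counted as a response to RSV vaccine given alone, it lowers the Control GMT and hence the ratio, toward the result the sponsor hopes for.

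The pathway is not fanciful. The ES codes keep such a person, the protocol allows further sampling, and Protocol Table 8 schedules RSV titers for all Control participants at Visits 2 and 3. If nominal Visit 2 is taken as baseline, the ANCOVA has both values it needs. The sentence on analysis by administered intervention does not help, because no COVID-19-only group exists. Co-Ad participants receive both vaccines at one visit, so a missed RSV dose is likelier in Control.

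The ES run is the plan's stated check that PPS exclusions do not drive the result. A check biased toward agreement would reassure too much. A lesser worry is that full-ES denominators for unsolicited events after the second dose would dilute Control rates.

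**Working it through.** **Inputs from the documents.** RSV SD 0.45 on the log10 scale, planning ratio 1.05, margin 1.5, 361 evaluable and 415 vaccinated per group, one-sided alpha 0.025 (SAP section 5, Table 3).

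**Assumed inputs.** The number k of Control participants with a Visit 3 sample but no RSV dose, and the RSV fold rise F, are not given. Protocol 7.1 describes permanent discontinuation of study intervention as rare. I take k = 4 or 8 (about 1% or 2% of 415) and F = 4 or 10.

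**The plan's own figure.** Distance to the margin: log10(1.5) − log10(1.05) = 0.1549. SE = 0.45 × √(2/361) = 0.0335. Power = Φ(0.1549/0.0335 − 1.96) = 99.6%, as in Table 3. Also 361/0.87 = 414.9, hence 415.

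**Shift in the ES ratio.** With x = k/415, the log10 Control mean falls by x·log10(F), so the ratio is multiplied by F^(−x). The Control variance becomes 0.45² + x(1 − x)(log10 F)², and the SE is √[(Control variance + 0.45²)/415]. With no undosed participants, SE = 0.45 × √(2/415) = 0.0312 and the 95% factor is 10^(1.96 × 0.0312) = 1.151.

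| k | F | Multiplier | Shift / SE | Upper limit, dosed-only ratio 1.30 | Upper limit, dosed-only ratio 1.05 |
|---|---|---|---|---|---|
| 0 | – | 1.000 | 0 | 1.497 | 1.209 |
| 4 | 4 | 0.987 | 0.18 | 1.478 | 1.194 |
| 4 | 10 | 0.978 | 0.30 | 1.466 | 1.184 |
| 8 | 4 | 0.974 | 0.37 | 1.459 | 1.178 |
| 8 | 10 | 0.957 | 0.60 | 1.437 | 1.160 |

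An ANCOVA simulation (415 per group, assumed covariate slope 0.5, 1,500 runs) gave the same multipliers.

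**When the ES reading would change.** The dosed-only upper limit must lie just above 1.5. Its ceiling is 1.519 in the mildest row and 1.563 in the strongest. Dividing by 1.151, the dosed-only ratio must fall between 1.303 and 1.319 (mildest) or 1.357 (strongest). If the true ratio is 1.05, an estimate of 1.303 lies (log10 1.303 − log10 1.05)/0.0312 = 3.0 standard errors away, a chance of about 0.1%.

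**What the text already says about dosed participants.**
- SAP 4.2.1 defines the RSV endpoint as a titer one month after RSV vaccine administration. Changing the analysis set does not change the endpoint.
- SAP 4.2.2 uses the timepoint one month after administration and adjusts for the pre-dose titer. SAP 4.1.2 takes baseline as the last value before the dose, and 6.3.5.2 drops anyone without a pre-vaccination titer from the ANCOVA. Without an RSV dose date there is, strictly, no such value.
- Protocol Table 8 labels Visit 3 as the sample after the RSV dose.
- The estimand table in SAP 1.1.1.1 lists vaccination not given per protocol as an intercurrent event and excludes later data.

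SAP 6.3.3 governs summaries by visit. It does not turn a sample from an undosed person into a post-dose sample.

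**Safety denominator.** With 8 of 415 undosed, 83 participants with an event give 83/415 = 20.0% on the full ES and 83/407 = 20.4% among those dosed. SAP 6.3.1 already ties events to the dose given.

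**The case for a change.** The strongest argument for a change is that none of these pointers is a rule for the ES. The RSV PPS spells out receipt of the RSV vaccine and the ES does not, so two programmers could differ. The estimand table cannot settle it alone: the ES run exists to bring back people whom the PPS removed, and applying the whole table would bring the ES close to the PPS again. The 5% trigger is also a realistic prospect, since planning allows about 13% non-evaluable, although that figure includes drop-outs without samples. At a true ratio of 1.5, the one-sided error of the ES comparison would rise from 2.5% to 3.9%–5.3% with 1% undosed, and to 8.2%–16.7% with 3% undosed (fold rise 4 to 12, assumed).

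The gap in wording and the usual direction of the shift both stand. The direction is not guaranteed, because a Co-Ad participant given only the COVID-19 vaccine also stays in the ES and pushes the ratio up. The error rates are conditional on a true ratio at the margin, on the trigger being met, on continued sampling, and on an analyst counting as post-dose a sample with no dose before it. They describe a complementary analysis that carries no claim. The 3% case means about 12 sampled but undosed Controls, which sits poorly with an event the protocol calls rare.

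**Conclusion.** No change is needed. The ES lacks an explicit per-vaccine receipt rule, but this is missing detail that analysts fill sensibly: the endpoint, covariate, baseline and estimand wording all lead to an RSV analysis of RSV recipients. The same holds for unsolicited-event tables by dose, where the difference is about 0.4 percentage points in the example.

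The confirmatory RSV result is protected by the PPS definition. The SARS-CoV-2 comparison is unaffected by a missed RSV dose in Control, because both groups receive that vaccine on Day 1. Only the conditional ES run for RSV-A and RSV-B could move. With 4 to 8 undosed Controls and a 4- to 10-fold rise, it moves by 1.3% to 4.3%, or 0.2 to 0.6 standard errors. Its reading would change only if the dosed-only ratio fell in a narrow band starting at 1.303, far from the planned 1.05. Both ranges are assumptions. A much larger number of sampled but undosed Controls would make the shift matter more, but nothing in the documents suggests one.
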